9.3. Randomization

Participants will be randomized in a ratio of 1:1 to each of the 2 treatment arms, Bi-26 or placebo.

A stratification blocking factor will be used in the ratio of 1:2 for $(WAZ \le -3):(-3 \le WAZ \le -2)$ within each treatment arm. Dynamic randomization algorithms will be used to balance treatment arms with respect to the other stratification factor levels (country, age at enrollment (Day 1), discharge destination) and ensure an overall treatment balance.

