9.7. Primary and Secondary Estimands

Participants randomized to the group receiving 28 days of Bi-26 will be compared to participants randomized to 28 days of placebo for the primary analysis.

Following International Council for Harmonization of Technical Requirements for Pharmaceuticals for Human Use (ICH) E9 (R1) addendum, the estimands relating to the study objectives are constructed by using the 5 following attributes:

- (a) treatment
- (b) population
- (c) variable/endpoint
- (d) population level summary
- (e) intercurrent events.

These attributes were specified to translate the study objective(s) into a treatment effect that is to be estimated (estimand). Refer to Table 4 and Table 5 for a summary of the primary and secondary estimands, respectively.

| Objective | Primary Estimand |
|---------------------------|-------------------------------------------------------------------------------------------------------------------------------------------------------------------------------------|
| To evaluate the change in | a. Population : The mITT population will be used for the analysis. |
| age) of infants receiving | b. Endpoint : WAZ change from baseline (Day 1) to the Day 56 visit in Bi-26 group. |
| B1-20 | c. Population level summary : Mean change from baseline in WAZ in the Bi-26 group compared to placebo with stratification blocking factors and feeding regimen covariate(s). |
| | d. Intercurrent event(s) : Including but not limited to treatment discontinuation. Further details will be specified in the SAP . |

Table 4: Primary Estimands

| Objective | Secondary Estimand | | | | |
|--------------------------------------------------|-------------------------------------------------------------------------------------------------------------------------------------------------------------------------------------------------------|--|--|--|--|
| To evaluate the change in | a. Population : The mITT population will be used for this analysis. | | | | |
| weight of infants receiving Bi-26 | b. Endpoint : weight change (in grams) from baseline (Day 1) to the Day 56 visit in Bi-26 group. | | | | |
| | c. Population level summary : Mean change from baseline in weight in the Bi-26 group compared to placebo with stratification blocking factors and feeding regimen covariate(s). | | | | |
| | d. Intercurrent event(s): Including but not limited to treatment discontinuation. Details will be provided in the SAP. | | | | |

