The weights used to assign the priority of balance to each factor is given by an integer value from 0 to 5 for each of the stratification variables (in this case WAZ, Age, Country, and Discharge destination) as well as for study (overall), stratum and site balance. The same weight is assigned to all levels of the stratification factors. The weights chosen for each of the relevant factors are presented in Table 3. The final choice of weights was also based on the simulations and expert input described above. High priority in balance is given to Study and WAZ as we aim for 1:1 ratio of treatments overall, and within WAZ strata.

The minimization algorithm determines the imbalance scores of assigning the next participant to be randomized to Bi-26 or Placebo. The treatment allocation least likely to cause imbalance based on these scores will be assigned.

The following formula is used to calculate the weighted imbalance score for treatment i:

$$Im_score_i = \sum_{j} w_j Im_{ij}$$

Confidential Page 16 of 50

where w_j is the weight associated with factor j and Im_{ij} is the relative imbalance due to assigning the next participant to be randomized to treatment i. The calculations for the different treatments are done separately, assuming the new participant is randomized to the respective treatment. Given that the target allocation between treatment groups is 1:1, that n participants have been randomized for factor j (in the level of the new participant), that m out of n participants have been assigned to treatment i, the relative imbalance for factor j and treatment i, Im_{ij} , is calculated as

$$Im_{ij} = 2 \times \left| 0.5 - \frac{m+1}{n+1} \right|$$

where

m: # participants already allocated to treatment i in factor j (relevant level)

n: # participants already randomized in factor j (relevant level)

Note that Im_{ij} is calculated assuming the n + 1th participant is randomized to treatment i.

Table 3. Weights Assigned to Factors Used in Dynamic Allocation

Factor	Weight
Study	3
Strata	1
Site	1
WAZ	3
Age	2
Age Country	1
Discharge destination	1

The final algorithm for treatment allocation of a participant is the following:

- 1. Determine the imbalance within factor, Im_{ij} , of assigning the next participant to treatment i, for each factor, given treatment allocations within each factor up to that point
- 2. Draw a random integer, say r_1 , between 0 and 100
- 3. If:

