11.5.2.1 Analysis of endpoint

WAZ will be summarized using descriptive statistics for actual and CFB values by visit and treatment group.

A MMRM will be used to estimate the difference in mean CFB between Bi-26 and Placebo, adjusting for covariates baseline WAZ, age (in days), country and discharge destination. The model will use CFB in WAZ as outcome and include the following effects:

- Fixed effects: Treatment, Visit (categorical), Treatment*Visit interaction, WAZ at baseline (continuous), Age (in days) at baseline, Country, Discharge destination
- Random intercepts: participant.

and will be fit using data from all planned follow-up visits where WAZ was measured, ie, Day 28, 56, and 90 visits. The adjusted interaction effects (Treatment*Visit) will be presented as estimates of the difference in CFB between treatment groups at each follow-up visit (Day 28, 56, and 90). The associated 95% CIs and p-values will be presented. PROC MIXED will be used to fit the models. SAS code for the models is provided in Appendix 3. If the WAZ score is not normally distributed, an appropriate transformation, such as the natural log, will be used as outcome for analysis. Normality will be investigated using q-q plots.

A participant listing of WAZ will be presented with actual values and CFB.

The descriptive table, model and listing will use the mITT population. The summary table will be repeated for the PP population.

Line graphs with the means and 95% CIs for WAZ will be presented by treatment group for visits Baseline, 28, 56, and 90.

Confidential Page 32 of 50

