11.5.3.1 Analysis of endpoint

Weight (grams) will be summarized using descriptive statistics for actual and CFB values by visit and treatment group. CFB values will be presented in the summary table in gram units. To obtain CFB in grams, weight (kg) as captured in the eCRF will be multiplied by 1,000.

The same model presented in Section 11.5.2.1 will be used to estimate the difference in mean CFB (in grams) between Bi-26 and Placebo at Day 56, adjusting for baseline weight (grams), age, country, and discharge destination. The adjusted interaction effects (Treatment*Visit) will be presented as estimates of the difference in CFB between treatment groups at each follow-up visit (Day 28, 56, and 90). The associated 95% CIs and p-values will be presented. PROC MIXED will be used for the analysis. Normality will be investigated using q-q plots. If weight is not normally distributed an appropriate transformation, such as the natural log, will be used as outcome for analysis.

A participant listing of weight will be presented with actual values (in kilograms and grams) and CFB (in grams).

The descriptive table, model and listing will be presented for the mITT population. The summary table will be repeated for the PP population.

Confidential Page 34 of 50

Line graphs with the means and 95% CIs for weight (grams) will be presented by treatment group for visits Baseline, 28, 56, and 90.

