11.5.6.1 Analysis of endpoint

The proportion of infants with WAZ > -2 at Day 56 with 95% CIs will be estimated and presented in a table by treatment group. The binomial mid-P method will be used to estimate the CIs.

Log-binomial regression will be used to estimate the risk ratio of WAZ > -2 rates at Day 56 between Bi-26 and Placebo, adjusting for the following covariates: baseline WAZ, age (in days), country and discharge destination. The adjusted risk ratio (exponentiated coefficient) with 95% CI will also be presented in the same summary table as the proportion estimates. If the overall rate is less than 15% of all participants or the log-binomial model does not converge, then logistic regression will be used in the place of log-binomial regression and odds ratios will be reported instead of risk ratios, which will be a reasonable estimate of the risk ratios. PROC GLIMMIX will be used for this analysis.

The Safety and PP populations will be used for this analysis.

Increases will be indicated as flags in the WAZ listing described in Section 11.5.2.1.

11.5.7 Re-hospitalization rates through Day 56

The number of re-hospitalizations for acute non-surgical illness by Day 56 per participant will be summarized using descriptive statistics and will be presented in a table by treatment group.

Negative-binomial regression will be used to estimate the incidence rate ratio of re-hospitalization at Day 56 between Bi-26 and Placebo, adjusting for the following covariates: baseline WAZ, age (in days), country and discharge destination. The adjusted rate ratio (exponentiated coefficient) with 95% CI will also be presented in the same summary table as the descriptive statistics.

The number and proportion of infants that were re-hospitalized for acute non-surgical illness by Day 56 with 95% CIs will be presented in a table by treatment group. The binomial mid-P method will be used to estimate the CIs.

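### The key secondary model for weight in grams has no baseline WAZ term, although its estimand calls for the stratification factors; the cost is slight imprecision and an undeclared mismatch

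*Protocol*

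**What the plan says.** The estimand: Protocol 9.7, Table 5, summarises the key secondary endpoint (change in grams to Day 56) as "Mean change from baseline in weight in the Bi-26 group compared to placebo with stratification blocking factors", together with feeding covariates. SAP Table 2 carries the same definition.

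The factor: Protocol 9.3 states "A stratification blocking factor will be used in the ratio of 1:2" and applies it to WAZ at or below -3 against WAZ between -3 and -2. Country, age and discharge destination are listed there as the other stratification factors. SAP 7.2.1 moves WAZ into the dynamic allocation but keeps its importance: "High priority in balance is given to Study and WAZ as we aim for 1:1 ratio of treatments overall, and within WAZ strata". In SAP Table 3, Study and WAZ have weight 3, age has 2, and every other factor has 1.

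The models: the primary model in SAP 11.5.2.1 lists "Fixed effects: Treatment, Visit (categorical), Treatment*Visit interaction, WAZ at baseline (continuous), Age (in days) at baseline, Country, Discharge destination". SAP 11.5.3.1 says the same model is used for grams, "adjusting for baseline weight (grams), age, country, and discharge destination". SAP 11.5.6.1, for recovery to WAZ above -2, fits its model "adjusting for the following covariates: baseline WAZ, age (in days), country and discharge destination"; the responder models (11.5.5.1) and re-hospitalization models (11.5.7) use the same set.

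SAP Section 9 declares two changes from the protocol: one to the randomization and one to the populations for secondary endpoints. Neither concerns the covariates of the grams model.

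**The concern.** The blocking-factor phrase can be read narrowly, as WAZ alone, or broadly, as all four stratification factors. WAZ belongs under either reading, yet it is the one stratification factor that the grams model does not name. SAP 11.5.3.1 also invokes the primary model, which contains baseline WAZ, and then gives a list without it. A reader cannot tell whether baseline weight was meant to replace WAZ or to be added to it.

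When allocation is balanced on a factor that predicts outcome and the analysis leaves it out, the treatment estimate stays unbiased. The standard error, however, still carries variance that the design has balanced away, so the interval is somewhat too wide. What is at stake is a little precision on the only key secondary endpoint, and an adjustment set that departs from the stated estimand without explanation.

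**Working it through.** **1. The plan's own figure.** The only sample size stated is for the WAZ primary (Protocol 9.4): difference 0.45, SD 1.3, two-sided 5%, power 90%. Normal approximation: n per group = 2 × (1.960 + 1.282)² × 1.3² / 0.45² = 175.4, so 176. The exact t calculation gives 177, as stated. No effect size, SD, sample size or power is stated for grams, so none depends on this point.

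**2. Stratification factors against model terms.**

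| Factor (allocation weight) | Primary model, 11.5.2.1 | Grams model, 11.5.3.1 |
|---|---|---|
| WAZ (3) | baseline WAZ, continuous | not named; baseline grams instead |
| Age (2) | yes | yes |
| Country (1) | yes | yes |
| Discharge destination (1) | yes | yes |

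**3. How much WAZ the grams model already carries.** SAP 11.5.1 computes WAZ from weight, age and sex. Weight and age are in the grams model; sex is not. The documents do not give the growth-standard parameters, so the following are assumptions: ages 30 to 120 days; all infants below -2 with one third at or below -3; S 0.12 to 0.14; L -0.1 to 0.25; median weight rising 30 to 60% over the age range; and a sex gap in median weight of 0 to 12%. Simulating 100,000 infants per scenario and regressing linearly gives these R² values:

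| Sex gap | Baseline WAZ on weight + age | WAZ stratum on weight + age |
|---|---|---|
| 0% | 0.98–0.99 | 0.66–0.68 |
| 5% | 0.92–0.95 | 0.62–0.65 |
| 8% | 0.83–0.89 | 0.56–0.60 |
| 12% | 0.69–0.78 | 0.47–0.53 |

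Adding sex raises the first column to 0.97–0.99 in every scenario. The binary stratum by itself explains about 0.65 of baseline WAZ. A different assumed growth curve gives 0.61 to 0.94 for weight plus age. WAZ is thus mostly but not fully represented, and the gap is mainly sex.

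**4. What adding WAZ gains.** Gain = 1 − MSE(with WAZ) / MSE(without), from least-squares regression of gram change on baseline grams and age. The slope of WAZ change on baseline WAZ was varied from 0 to -0.4, and the SD of WAZ change from 0.6 to 1.3.
- Across several assumed growth curves the gain runs from 0 to an upper end of 3.4%, 4.3% or 5.8%.
- At the protocol's SD of 1.3 it is about 1% or less (0.01 to 1.1% in one set of runs).
- I repeated this on the step 3 grid (200,000 infants per scenario, mean WAZ change 0.3, 55 days of follow-up). For sex gaps up to 8% the gain is at most 5.0% at SD 0.6 and 0.8% at SD 1.3. Only the 12% gap goes beyond the ranges above, reaching 9.3% and 1.6%.

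**5. Effect on the standard error.** Ratio = 1/√(1 − gain). At 6% it is 1/√0.94 = 1.031, or 3% too large. At 1% it is 1/√0.99 = 1.005, or 0.5% too large. In the 12% gap extreme, 1/√0.907 = 1.05.

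**The case against.** The strongest reply is that each change-from-baseline outcome is adjusted for its own baseline. The WAZ primary uses baseline WAZ, the gestational-age version (SAP 11.5.2.4.3) uses its own recalculated baseline, and grams uses baseline grams. The endpoints that keep baseline WAZ are either derived from WAZ or, like re-hospitalization, have no baseline of their own. That stands as a reason to keep baseline weight. It is no reason to leave WAZ out, since both can be in the model, and the SAP nowhere says that weight and age are meant to stand in for it.

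It can also be said that most of the possible gain is really the absent sex term. That largely stands. Wherever adding WAZ cut residual variance by more than 1.6%, adding sex alone cut it more, and with sex included WAZ added at most 1.6%. But WAZ is the factor the estimand and the allocation name, and adding it brings in the sex information as well.

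A reader might infer that the comparison ignores the main stratification factor. The documents do not support that: weight and age are two of the three inputs to WAZ and carry most of it. A reader might also turn a gain near 6% into about 20 of the 354 infants. That does not hold either. The 354 belongs to the WAZ endpoint, the 6% is near the top of a range that starts at zero, and the calculation is an ordinary regression rather than the planned repeated-measures model.

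**Conclusion.** The mismatch is real and minor. WAZ is a stratification factor with joint highest allocation weight, the key secondary estimand calls for it, and the grams model contains it only indirectly, with no declaration in SAP Section 9. The cost is a standard error that may be up to about 3% too large under most of the illustrative assumptions, and about 0.5% at an SD of 1.3. These sizes rest on assumed growth parameters, an assumed sex gap and an assumed slope on baseline WAZ. The smallest gains are effectively zero, and only a 12% sex gap takes them above the stated ranges. Nothing here implies bias or an inflated type I error: leaving out a balanced prognostic factor makes the test slightly conservative. The case for acting rests mainly on making the model agree with its estimand, because the correction is almost free.

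**What to change.** In SAP 11.5.3.1, add baseline WAZ (continuous, as in 11.5.2.1) or the WAZ stratum, keeping baseline weight, age, country and discharge destination. The continuous form recovers more: on the step 3 grid the stratum gained at most 4.0%, against 9.3% for continuous WAZ. Overlap between WAZ and baseline weight does no harm, because neither coefficient is of interest. The cost is one degree of freedom, a variable already computed in EDC for randomization, and a wording change to be made before unblinding.

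If the sponsor prefers to leave WAZ out, SAP 11.5.3.1 should say that baseline weight and age stand in for it, and Section 9 should list the departure. The same edit is a good place to reconcile the feeding covariates in the same estimand cell. They appear in neither main model; the breast-milk proportion enters only a sensitivity analysis of the WAZ model (SAP 11.5.2.4.2).

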9.7.1. Other Secondary Analyses

The safety of Bi-26 supplementation will be evaluated through EoS in the Safety population, which includes, but is not limited to, the frequency (and percentages) of AEs, and all SAEs through the Day 90 visit. Individual results and descriptive statistics will be provided by treatment group.

Individual results and descriptive statistics for presence of *B. infantis* in stool will be provided at each time point by treatment group.

9.7.2. Exploratory Analyses

The stool and blood biomarkers at specified timepoints will be analyzed using descriptive statistics.

Refer to Section 8.6 for biomarker testing. Details of the exploratory biomarker analyses, including potential additional exploratory engraftment analyses, will evolve from the initial test set to potential verification set. These will be included in separate operational and/or analysis plans. Results of these additional exploratory objectives may be reported separately from the main clinical study report.

10. Supporting Documentation and Operational Considerations

10.1. Regulatory, Ethical, and Study Oversight Considerations

10.1.1. Regulatory and Ethical Considerations

This study will be conducted in accordance with the protocol and with:

- consensus ethical principles derived from international guidelines including the Declaration of Helsinki and CIOMS International Ethical Guidelines
- applicable ICH GCP Guidelines
- applicable laws and regulations.

The protocol, protocol amendments, ICF, and other relevant documents (e.g., advertisements) must be submitted to an EC/IRB by the investigator and reviewed and approved by the IRB/EC before the study is initiated.

Any amendments to the protocol will require EC/IRB approval and approval by health authorities where applicable, before implementation of changes made to the study design, except for changes necessary to eliminate an immediate hazard to study participants.

The investigator will be responsible for the following:

Providing written summaries of the status of the study to the EC/IRB annually or more frequently in accordance with the requirements, policies, and procedures established by the IRB/EC

Notifying the IRB of SAEs or other significant safety findings as required by EC/IRB procedures.

Providing oversight of the conduct of the study at the site and adherence to requirements of ICH guidelines, the EC/IRB, and all other applicable local regulations.

10.1.2. Financial Disclosure

Investigators and sub-investigators will provide the sponsor with sufficient, accurate financial information as requested to allow the sponsor to submit complete and accurate financial certification or disclosure statements to the appropriate regulatory authorities. Investigators are responsible for providing information on financial interests during the course of the study and for 1 year after completion of the study.

10.1.3. Informed Consent Process

The investigator or his/her representative will explain the study to the participant's parent(s)/legal guardian and answer all questions regarding the study. The participant's parent(s)/legal guardian must be informed that their participation is voluntary.

The participant's parent(s)/legal guardian will be required to sign a statement of informed consent that meets the requirements of local regulations, ICH guidelines, and the ECs/IRBs or study centers.

Note that the participant's mother is the preferred individual to sign the informed consent given the protocol requirements for some feedings to be from breast milk and for collection of information on maternal antibiotic and probiotic usage.

However, the participant's other parent or legal guardian can provide consent if necessary. If the mother is not the consenting parent, the study requirements should be reviewed with the participant's mother to ensure understanding of study activities and ability/willingness to comply. The participant's mother will also sign the ICF for collection of her medical information described in the protocol.

The medical record must include a statement that written informed consent was obtained before the participant was screened and enrolled in the study and the date the written consent was obtained. The authorized person obtaining the informed consent must also sign the ICF.

Participant's consenting parent(s)/legal guardian must be re-consented to the most current version of the ICF during their infant's participation in the study.

A copy of the ICF must be provided to the participant's parent(s)/legal guardian prior to any study-related procedure.

Any withdrawal of consent for sample testing will be documented in the eCRF.

Refer to Section 5.3 regarding rescreening.

10.1.3.1. Informed Consent Form

Participant's consenting parent/legal guardian will be told that they are free to refuse to have their infant participate and may withdraw their consent at any time and for any reason during the study period. Any test results from the samples collected before withdrawing consent may still be used for the study.

The informed consent form will be obtained using a written ICF approved by the IRB/EC and signed and dated by the participant's consenting parent/legal guardian.

The ICF will contain a separate section that addresses the use of remaining mandatory samples for optional exploratory biomarker research. The investigator or authorized designee will explain the objectives of the exploratory research to the participant's consenting parent/legal guardian.

Participant's consenting parent/legal guardian must agree to the exploratory research; otherwise the participant cannot be in the study.

